4.5 Safety Population

The primary analysis of safety outcomes will be analysed using the safety population. The safety population will be comprised of the all individuals that received at least one injection of either the active dose or the placebo, with individuals that received any injections of the active dose being in the mepolizumab arm.

4.6 Other Analysis Populations

N/A.

5 General Issues for Statistical Analysis

Continuous Outcome data with symmetric distribution will be described with summary statistics such as the mean and standard deviation (SD). Skewed continuous Outcome data will be described using the median and interquartile range (IQR). Determination of symmetry will be made informally by visualisation, taking into account sample size for each variable, the nature of potential outliers, and similarity between mean and median values (recognising formal statistics to test for normality often lead to spurious results).

Categorical Outcome data will be summarised with numbers (absolute frequency) and percentages.

Summary tables for both continuous and categorical outcome data will be presented by treatment group and overall in the intention to treat population.

For continuous outcomes that follow a normal distribution, we will compute the adjusted mean change from baseline for each treatment arm, presenting it alongside the corresponding 95% confidence interval.

For non-normally distributed continuous outcomes, and if transformations prove ineffective in enhancing normality, we will resort to a non-parametric approach—specifically, the Wilcoxon rank-sum test (Mann-Whitney two-sample statistic) to compare outcome values between the two treatment arms at each time point without applying baseline adjustments. The calculated statistics will include the median, interquartile range, as well as the minimum and maximum values for each treatment arm.

All time to event analyses will be accompanied by Kaplan-Meier survival curves to compare the survival rate between the two groups.

To visually represent non-normally distributed outcomes, we will create a whisker plot, illustrating the median along with the 25th and 75th percentiles, minimum, and maximum values for each treatment arm.

For visual representation of all other normally distributed continuous outcomes, line plots will be produced for the adjusted mean change from baseline in each treatment arm alongside a 95% confidence interval using time since randomisation on x-axis and adjusted mean change from baseline at y-axis.

5.1 *Derived/ Computed Variables*

Treatment allocation received

The reason for Protocol deviation concerning participants who received incorrect trial drug/placebo and the treatment allocation variables will be used to derive a binary

variable that will indicate whether participants received/did not receive their randomised allocation.

Time window in between dosing visits

The actual date of dosing visits (1-12) corresponding to each participant will be used to derive a continuous variable that will represent the time window or intervals (measured in days) between doses.

Number of taken doses over 48 weeks (for truncated follow-up over minimum 24 weeks)

The binary variable of “dose administered (yes/no)” at each dosing visit (1-12) will be used in order to derive a count variable that will represent the number of taken doses during the Trial.

Modification in the prescribed dosage during Trial

The reason for Protocol deviation concerning participants who did not receive the correct dose of trial drug/placebo will be used to derive a binary variable that will indicate whether participants had a modification in their prescribed dosage.

Change in the mode of administration of Trial drug/placebo

The site of injection recorded at each dosing visit will be used to derive a binary variable that will indicate whether there has been a change in the mode of administration of the Trial drug/placebo over the course of 48 weeks (Participants consented to the truncated follow-up will receive minimum 24 weeks follow-up).

5.2 Multiple Testing

No corrections for multiple testing will be made as this trial has a single primary outcome.

5.3 Analysis Software

All clinical data will be extracted from a MACRO database.

It is anticipated that the statistical analysis will be performed using a current version of either STATA, SAS, or R (Versions will be recorded in the end of trial report).

6 Statistical Methodology

The statistical analysis will be based on external guidelines (e.g. ICH E3 and E9).

The date of data extraction will be included in the Statistical Report.

6.1 Disposition

Disposition of participants will be presented on the ITT population with respect to the number of randomised participants, completion status, reason for non-completion, treatment completion as per Protocol, number of doses received, protocol deviations and blinding status. Results will be tabulated and summarised over time by treatment group and overall.

A Consolidated Standards of Reporting Trials (CONSORT) diagram will display the flow of participants through the Trial (schulz et al, 2010).

A graph of cumulative recruitment will be presented in addition to summaries of recruitment (e.g. start and end date).

Data completeness (i.e. CRF return rate) will also be summarised by treatment group and overall for each CRF.

A swimmer plot of participants' treatment duration along with reasons for discontinuation of treatment will be produced per treatment arm.

6.2 Demographic and Baseline Characteristics

Demographics, baseline characteristics and medical history will be summarised by treatment group and overall. This will include the summary of the stratification factors: baseline eMRC dyspnoea stable state (≤ 3 , > 3) and number of past hospitalisations in the previous 12 months (0, ≥ 1).

Numbers (with percentages) for binary and categorical variables, and means (with standard deviations) where data meets the normality assumptions or medians (with lower and upper quartiles) if otherwise will be presented. Where data is log transformed improve normality and allow for parametric testing the geometric mean on the original scale (i.e. after anti-logging the calculation of the mean on the log scale) must be presented alongside standard deviations on the log scale.

There will be no tests of statistical significance nor confidence intervals for differences between randomised groups on any baseline variable.

6.3 Treatment Adherence

The numbers (with percentages) of participants receiving treatment doses 1 through 12, duration of total treatment period (last dose – first dose / 7) in weeks, numbers and duration of treatment delays will be reported descriptively between the intervention and placebo arms. The proportion of participants receiving doses at each visit will be presented in Bar diagram, showing dose number on y-axis and percentage of participants on the x-axis. The number of doses received per participant will also be presented graphically.

6.4 Primary Outcome Analysis

6.4.1 Primary Analysis of Primary Outcomes

The primary analysis will take place on the intention to treat population. All participants will be included in the model using censored values for participants not experiencing an event during their follow-up period.

The primary analysis will fit the Cox proportional hazard model for the primary outcome of the time to re-hospitalisation or death (any cause) as the dependent variable, treatment group as an explanatory factor and baseline MRC dyspnoea score (≤ 3 , > 3) and past hospitalisation in the previous 12 months ($(0, \geq 1)$) (Stratification factors). This analysis will be accompanied by Kaplan-Meier survival curves alongside with log rank test to compare the survival rate between the two groups. A hazard ratio (HR) of the mepolizumab relative to placebo, with their associated two-sided 95% confidence interval and p-values will be reported. A p-value ≤ 0.05 will be considered as significant difference.

Time until event (re-hospitalisation or death from any cause) will be measured in days from randomisation until re-hospitalisation, death or 12-month follow-up assessment, whichever happens first. Participants with no event (no re-hospitalisation or alive) assessed during follow-up visits will be censored at the last assessment date free from event.

Participants who do not complete the 12-month follow-up will be included in the primary analysis; those without a recorded event will be censored. Participants who withdraw from the trial will be censored at the date of withdrawal and participants lost to follow up will be censored at the date last assessment.

Proportional hazard assumption for the Cox proportional hazard model will be checked using the statistical tests and graphical diagnostics based on the Schoenfeld residuals.

Where participants don't reach the 12 month assessment but do not experience an event the last date of assessment known to be event-free will be used as the censor

value (right censoring). This will apply to participants who are withdrawn and/or lost to follow-up for any reason or receive truncated follow-up as part of the revised protocol. In the event of encountering multiple events occurring at the same time t , Efron's method for dealing with tied survival times will be implemented when fitting the Cox model to the data.

The KM plot will illustrate survival times over time including numbers at risk and number of events at regular time intervals, median survival estimates and survival estimates at 48 weeks follow-up for both intervention and placebo groups. Contrary to the protocol, the logrank test statistic will not be presented alongside the KM plot. The only test statistic to be presented will be that associated with the treatment term in the Cox model which will be used to test the hypothesis that the hazard of an event is different in the mepolizumab arm compared to the placebo arm.

The hazard ratio (HR) and associated 95% confidence interval will be presented.

A value of 1.0 would indicate the same hazard ratio in the intervention arm as placebo; a value below 1.0 would indicate a reduction in the hazard ratio of the event in the intervention arm, whereas larger values would infer a greater hazard ratio.

Lastly, an assessment of the Cox model residuals will be made by producing the following plots:

- Martingale residuals plot: to test for non-linearity of continuous covariates.
- Deviance residuals plot: to evaluate deviation from the saturated model.
- Cox-Snell residuals plot: to assess Goodness-of-Fit.

If the proportional hazards (PH) assumption does not hold in Cox proportional hazards regression, we will consider using flexible parametric survival models, such as the Royston-Parmar model or other parametric survival models. These models allow for more flexibility in modeling the baseline hazard, which can capture non-proportional hazards.

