7.8 Withdrawal criteria

Specified criteria for discontinuation of trial treatment will be for participants that miss more than one dose of the trial treatment or who delay a dose for >4 weeks. The only exception will be when this delay is due to a COPD exacerbation resulting in hospitalisation, in which instance the next dose will be administered at the next due date or as soon as possible afterwards to allow the participant to recover.

Every effort should be made by the research team to keep the participants in the trial. However, participants have the right to withdraw their consent to take part in the trial at any time without having to give a reason and this will not affect their future care. Withdrawal of consent details and reasons (if known) should be recorded on the CRF and in the medical notes.

The investigator may discontinue treatment of a participant at any time if they are not compliant with the trial protocol or to protect the participant's safety and well-being after consultation with the CI. The IMP may also be discontinued in the case of an adverse event which the investigator considers sufficient to jeopardise the safety of the participant. Participants who want to discontinue trial treatment should be encouraged to remain in the trial and

to continue to be followed-up as per the protocol or as per routine care. Participants who discontinue treatment, for whatever reason, will be asked for their consent to continue collecting data, as a minimum this must include data on hospital admissions and deaths for the remainder of the trial (48 weeks) in order to answer the primary outcome. Those declining this will be withdrawn from the trial (thus withdrawing their consent).

Every effort should be made to keep the participant in the trial to collect important efficacy and safety data. Additionally, there are a number of trial assessments (e.g. Quality of Life measures/Symptom Assessments) that may be collected over the telephone if the participant agrees to be contacted. Withdrawals from the trial should be discussed with the CI or their deputy and the Trial Manager. If a participant has withdrawn/discontinued from the trial for any reason, then his/her screening and trial ID number(s) cannot be issued to another participant.

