7.11 End of trial

This trial will end when the specified number of participants have been recruited, all participants have completed their last follow up visit, data validation has taken place and the database is locked and statistical analysis complete.

Data reported in the final report to REC and MHRA within 12 months of the End of Trial will include the primary and secondary outcomes (see sections 3.3.1 and 3.3.2).

Participants who become lost to Follow Up will be followed-up via their hospital records until 48 weeks to collect information on the number of exacerbations, number of hospitalisations and death. Those consented to truncated follow-up (consented to study from July 2023 onward) will be followed-up via their hospital records until their Final Follow-up visit which will occur 4 weeks \pm 7 days from what would have been their final dosing visit (based on when they are consented to the trial).

The trial will be stopped prematurely if:

- Mandated by the Ethics Committee or the Sponsor
- Mandated by the Medicines and Healthcare products Regulatory Agency (MHRA)
- Following recommendations from the Data Safety Monitoring Committee (DSMC) or otherwise the Trial Steering Committee (TSC) determine the trial should stop
- Funding for the trial ceases

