3.1 Primary Outcome

3.1.1 Definition and Derivation of Primary Outcome

Time from randomisation to next hospital readmission or death (all cause).

The time from randomisation to next hospital readmission or death (all cause) is defined as a time to event outcome measured in days. The date of randomisation as well as the date of readmission or death (whichever occurs first) will be used to calculate time to event. For participants not experiencing an event the time will be calculated from randomisation until last known follow-up assessment event-free. A variable to indicate event (with a value of 1) or no event (with a value of 0) will be derived. Details of the primary outcome analysis are included in section 5.5.

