The time from randomisation to treatment failure is defined as a time to event outcome measured in days. The date of randomisation and dates of treatment intensification and increase in hospital care (whichever is the latter) will be used to calculate time to event. Participants not experiencing both treatment intensification and increased hospital care will have time measured from randomisation until last known follow-up assessment event-free. A variable to indicate event (with a value of 1) or no event (with a value of 0) will be derived.

- Time from randomisation to death (all cause)

The time from randomisation to death (all cause) is defined as a time to event outcome measured in days. The date of randomisation and the date of death will be used to calculate time to event. For participants with no known death date the time will be calculated from randomisation until last known follow-up assessment. A variable to indicate event (with a value of 1) or no event (with a value of 0) will be derived.

- Time from randomisation to death (respiratory cause)

The time from randomisation to death (respiratory cause) is defined as a time to event outcome measured in days. The date of randomisation and the date of death where cause is defined as respiratory will be used to calculate time to event. For participants with no known death date the time will be calculated from randomisation until last known follow-up assessment. For participants with a date of death attributed to other (non-respiratory) causes the time will be calculated from randomisation until death. A variable to indicate event (with a value of 1) or no event (with a value of 0) will be derived.

- Time from randomisation to next hospital readmission (all cause)

The time from randomisation to next hospital readmission (all cause) is defined as a time to event outcome measured in days. The date of randomisation and the date of next hospital readmission following randomisation will be used to calculate time to event. Where hospital readmission doesn't occur during follow-up, time will be measured until the participant's last known follow-up assessment. A variable to indicate event (with a value of 1) or no event (with a value of 0) will be derived.

- Time from randomisation to next hospital readmission (respiratory cause)

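### The plan collects admissions and deaths from hospital records to week 48 but ends event-free time at the last assessment, so the primary endpoint has no single follow-up window

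*SAP*

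**What the plan says.** **Collection.** Protocol 7.11: "Participants who become lost to Follow Up will be followed-up via their hospital records until 48 weeks". The information includes hospitalisations and death. For the truncated cohort, records are followed to the scheduled Final Follow-up. Protocol 7.8 asks participants who stop treatment to allow continued data collection, and "as a minimum this must include data on hospital admissions and deaths for the remainder of the trial (48 weeks", with the primary outcome given as the reason. SAP 4.2 and Protocol 10.7 include the outcome data obtained from all participants.

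**Events.** SAP 3.1.1: "The date of randomisation as well as the date of readmission or death (whichever occurs first) will be used to calculate time to event". It sets no limit relative to the last assessment.

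**Event-free time.** SAP 3.1.1: "For participants not experiencing an event the time will be calculated from randomisation until last known follow-up assessment event-free". SAP 6.4.1 says that "those without a recorded event will be censored", and then that "participants lost to follow up will be censored at the date last assessment". It adds a last-event-free-assessment rule: "This will apply to participants who are withdrawn and/or lost to follow-up for any reason or receive truncated follow-up as part of the revised protocol". Protocol 10.3.2 has the same censoring rule for lost participants; Protocol 10.8 allows the date last seen as an alternative. For all-cause death, SAP 3.2.1 uses the death date and otherwise: "For participants with no known death date the time will be calculated from randomisation until last known follow-up assessment".

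Neither document says that a clear records check extends event-free time. SAP 6.4.3 plans no sensitivity analysis of the primary outcome.

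**The concern.** Take two participants last assessed at week 12. One is readmitted at week 30 and the records show it. The other has clear records to week 48.

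- **Reading 1: record-found events count.** The first is an event at week 30, having been at risk throughout. The second is censored at week 12. Membership of the risk set from week 12 to week 30 is decided by what happens later, so the rule itself makes censoring informative.
- **Reading 2: lost participants are always censored at last assessment.** Both are censored at week 12. That is consistent, but it discards data which Protocol 7.8 and 7.11 collect and which SAP 4.2 says will be analysed.

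The outputs at stake are the primary HR and the 48-week Kaplan-Meier estimates (SAP Table 4). The time-to-death and time-to-readmission outcomes use the same rule. The trial statistician has access to allocation, so the choice should be fixed before the data are analysed.

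**Working it through.** **Inputs from the plan** (Protocol 10.1, SAP 2.2.3): placebo event proportion 0.65 at 48 weeks, HR 0.6, power 0.8, alpha 0.05 (two-sided, SAP 6.4.1), 1:1 allocation, 226 analysed, 238 recruited.

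**Assumptions.** The documents give no rate of loss after the first dose; their 5% covers only participants never dosed. I take 5–20% loss (15% and 25% for deaths), uniform over 48 weeks and independent of outcome, with the last assessment on the 4-weekly visit grid and exponential event times.

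**1. Reproduce the plan's figure (Freedman).**
- Events = (1.96 + 0.842)² × (1.6/0.4)² = 7.85 × 16 = 125.6, so 126.
- Mepolizumab event proportion = 1 − 0.35^0.6 = 0.467; mean of the arms = 0.559.
- 126 / 0.559 = 225.5, so 226; 226 / 0.95 = 237.9, so 238. Both match.
- Expected events in 238 = 119 × (0.65 + 0.467) = 133.

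**2. Reading 1, by large-sample simulation (true HR 0.60).**

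| Loss, placebo / mepolizumab | Placebo risk at 48 weeks | Mepolizumab risk at 48 weeks | HR |
|---|---|---|---|
| none | 0.65 | 0.467 | 0.60 |
| 5% / 5% | 0.658 | 0.475 | 0.601 |
| 10% / 10% | 0.665 | 0.483 | 0.605 |
| 20% / 20% | 0.682 | 0.501 | 0.607 |
| 10% / 20% | 0.664 | 0.500 | 0.629 |
| 20% / 10% | 0.680 | 0.483 | 0.583 |

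With a front-loaded hazard (Weibull shape 0.55) the last two HRs are 0.621 and 0.585. With true HR 1, loss of 20% against 10% gives an HR of 0.963. Loss of 30% against 10% gives 0.94 and a type I error of 0.073, against 0.057 under a common window in the same run (Monte Carlo error about 0.004).

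**3. Deaths under reading 1.** The mean last-visit week for lost participants is 22 (grid 0, 4, …, 44), so a lost survivor forfeits 26/48 = 0.542 of the follow-up. If deaths are few, the rate is inflated by about 1/(1 − loss × 0.542):
- 15% loss: 1/(1 − 0.081) = 1.09
- 25% loss: 1/(1 − 0.135) = 1.16

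Participants who die keep their full time, which lowers this slightly. Simulation at 6–12% mortality gives about 8% and 14–15%.

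**4. Reading 2.** The HR stays at 0.60 because loss was assumed independent of outcome. Among lost participants, the share with an event after the last visit is the mean of S(g) over the visit grid minus S(48):
- Placebo: 0.647 − 0.350 = 0.297
- Mepolizumab: 0.762 − 0.533 = 0.229

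Events discarded in 238 = loss × 119 × (0.297 + 0.229) = loss × 62.6, or about 6 at 10% and 12.5 at 20%. If events between the last visit and the moment of loss are kept, the 20% figure is about 11.

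Freedman power at 226 = Φ(0.25 × √events − 1.96), with events scaled by 226/238:
- 10% loss: 127 events become 120.6; Φ(0.785) = 0.78
- 20% loss: 121 events become 114.9; Φ(0.72) = 0.76

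**5. Common window.** With records used for both events and event-free time, the HR is 0.60, the risks are 0.65 and 0.467, there are 133 events, and power at 226 is 0.80.

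**The case against.** A reader might infer that the plan commits to reading 1 and that the primary HR is therefore biased. The documents do not support that. The SAP never names hospital records as the event source; that follows only from putting Protocol 7.8 and 7.11 beside SAP 4.2. The sentence on lost participants in SAP 6.4.1, taken alone, is reading 2, under which the HR is unbiased if loss is non-informative. Even under reading 1 a balanced loss moves the HR by about 0.01 or less. The larger shifts need a two-fold imbalance in a double-blind trial, at loss rates that the documents do not state.

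Nor do the documents tie censoring strictly to visit attendance: the SAP says assessment, and Protocol 10.8 allows last seen. Few participants need be affected, since those who stop treatment but remain in the trial are invited to the final visit (Protocol 7.7.4).

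There is also a case for stopping at the last date known to be event-free. Protocol 7.11 says only hospital records, and Protocol 5 claims over 95% coverage for COPD exacerbation admissions in Leicestershire, not for all-cause admissions or deaths elsewhere. If records caught 70% of events after loss (an assumption), using them would give an HR of about 0.62 (20% placebo, 10% mepolizumab loss) or 0.59 (reversed).

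These points limit the size of the problem and justify a sensitivity analysis. They do not supply the missing censoring date: reading 2 still conflicts with the stated purpose of the records follow-up, and reading 1 still makes censoring depend on outcome.

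**Conclusion.** The concern holds as a mismatch between the event window and the event-free window of the primary endpoint, with two readings open and neither satisfactory.

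- **Reading 1:** 48-week risks are overstated by about 1.5 to 3 percentage points at 10–20% loss. The HR is nearly unaffected by balanced loss and shifts by about 0.02–0.03 at 10% against 20%. Death rates are inflated by about 8% at 15% loss and 14–15% at 25%.
- **Reading 2:** the HR is unbiased only under non-informative loss. About 6 events at 10% loss and 11 to 12 at 20% are discarded out of 133, and power falls from 0.80 to about 0.78–0.76.

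All the loss rates are assumptions. Only participants who have not withdrawn consent to data collection and have no final assessment are affected. This could include randomised participants never dosed (5% of 238 is about 12): they stay in the intention-to-treat set and, with no later assessment, would be censored near day 0 if event-free.

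**What to change.** In SAP 3.1.1, 3.2.1 and 6.4.1, and in Protocol 10.3.2 and 10.8:

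1. Define one follow-up window for events and event-free time. It ends at the earlier of the planned end of follow-up (week 48, or the scheduled truncated Final Follow-up date) and the date hospital records were last checked.
2. Count only events inside that window. Without this limit, events found after the window would recreate the mismatch.
3. Censor event-free participants at the end of the window, whether or not they had a final assessment. Where consent to data collection was withdrawn, censor at the withdrawal date.
4. In SAP 6.4.3, add a sensitivity analysis that ends both events and event-free time at the last assessment, because records may miss admissions or deaths elsewhere.

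The cost is SAP and protocol wording plus a field for the date records were last checked. The records review is already planned, and the sample size of 226 analysed and 238 recruited is unchanged.

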2.2.3 Sample size

Readmission rates at 6, 9 and 12 months were 51%, 59% and 64% respectively for patients admitted with a diagnosis of COPD (ICD code: J44) in Leicestershire in 2015. This is in line with national data from the HQIP RCP National COPD audit (2014) which had a readmission rate of 43% at 3 months. In addition, 6% of patients discharged from hospital with an exacerbation of COPD died in the 12 months following admission without hospital readmission.

National UK data from the HQIP funded RCP/BTS National COPD audit (2014; data unpublished) showed 24.9% patients had an eosinophil count of ≥ 300 cells/ μL on admission. In patients with an eosinophil of ≥ 300 cells/ μL on admission ($n=1,587$), 46.1% of patients were readmitted within 3 months of initial hospitalisation, similar to the non-eosinophilic COPD population.

Assuming 65% of patients receiving usual care will have an event by 48 weeks (composite endpoint: hospitalisation or death) and those treated with mepolizumab have a hazard ratio of 0.6, then 226 patients (113 per group) would be required to show a statistical difference power 0.8, $\alpha=0.05$). We have also assumed 5% drop-out (recruited but not receiving first dose) and therefore the final recruitment target of 238 patients.

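### The SAP's fallback for failed proportional hazards is justified only by a flexible baseline hazard; unless a time-varying treatment effect or a non-PH scale is specified, it does not address non-proportionality

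*SAP*

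**What the plan says.** The primary analysis (SAP 6.4.1, Protocol 10.3.2) is a Cox model with a treatment term and the two stratification factors. Both documents check PH with tests and plots of Schoenfeld residuals. Neither gives a threshold for calling the assumption failed.

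Only the SAP has a fallback. If PH does not hold, it will consider flexible parametric models, naming Royston-Parmar and leaving room for other parametric forms. Its explanation is: "These models allow for more flexibility in modeling the baseline hazard, which can capture non-proportional hazards". It names no treatment-by-time term, model scale, knots, degrees of freedom or alternative effect measure.

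The same section limits testing: "The only test statistic to be presented will be that associated with the treatment term in the Cox model". It also plans Kaplan-Meier curves with numbers at risk, medians, and 48-week survival estimates for each arm. The template for Table 4 (SAP Appendix 1) puts the 48-week estimates beside the HR.

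**The concern.** The fallback is meant for the case where one hazard ratio does not describe the treatment effect. Its stated mechanism relaxes something that Cox never constrained. An analyst who followed it literally would refit nearly the same hazard ratio with a smoother baseline and could report that non-proportionality had been handled.

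Nothing else in the plan fills the gap:

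- SAP 6.4.2 (per-protocol analysis) reuses the same model.
- SAP 6.4.3 plans no sensitivity analysis of the primary outcome.
- The stratified Cox model in SAP 3.4 and 6.6 and Protocol 10.4 lets the baseline differ between strata. It does not let the treatment effect differ over time.
- SAP 6.5.1 and 6.5.1.1 carry the primary method over to every time-to-event secondary outcome, so the gap goes with it.

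At stake is the interpretation of the primary result if the check fails. Any model form that does address the problem would have to be chosen after the data are seen. The trial statistician has access to the allocation list (Protocol 7.4, SAP 2.2.4), so it is better to fix that form beforehand.

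**Working it through.** **1. The plan's own figure.** SAP 2.2.3 gives the inputs: "Assuming 65% of patients receiving usual care will have an event by 48 weeks", "those treated with mepolizumab have a hazard ratio of 0.6", and the result "then 226 patients (113 per group) would be required to show a statistical difference power 0.8", with alpha 0.05.

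- Freedman events: (1.960 + 0.842)² × [(1 + 0.6)/(1 − 0.6)]² = 7.85 × 16 = 125.6, so 126.
- Treated event rate: 1 − 0.35^0.6 = 46.7%. Average of the arms: (65% + 46.7%)/2 = 55.9%.
- N = 126/0.5587 = 225.5, so 226. With 5% drop-out, 226/0.95 = 237.9, so 238.

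The stated size reproduces. It assumes one constant HR and is not affected by this point.

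**2. The algebra.** Let x = 1 for mepolizumab.

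- Cox: h(t|x) = h₀(t)·exp(βx), with h₀ unspecified. The hazard ratio is exp(β) at every t.
- Royston-Parmar, hazard scale, baseline spline only: ln H(t|x) = s(ln t) + βx. Then H(t|1) = exp(β)·H(t|0). Differentiating, h(t|1)/h(t|0) = exp(β) at every t. However flexible s is, this is a PH model.
- With a treatment-by-time term: ln H(t|x) = s(ln t) + βx + x·g(ln t). Then HR(t) = exp[β + g(ln t)] × [s′(ln t) + g′(ln t)]/s′(ln t), which can change with t.

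**3. Size, by simulation.** From the plan: N = 238, 1:1 allocation, and a control hazard of −ln(0.35)/48 = 0.0219 per week. Assumptions not in the documents: the control hazard is constant; the HR changes at week 12 by the amounts shown; one sixth of patients are truncated to 24–44 weeks; and two binary covariates are fitted but have no effect on the hazard. Values are medians over 60 trials (40 for the constant HR). The baseline spline has 3 df and the time-dependent term 2 df.

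| Assumed true HR | Cox | Royston-Parmar, baseline spline only | With treatment-by-time term: week 4 | week 36 |
|---|---|---|---|---|
| 0.6 throughout | 0.615 | 0.614 | 0.59 | 0.63 |
| 1.0, then 0.4 | 0.606 | 0.604 | 1.02 | 0.39 |
| 0.4, then 1.0 | 0.788 | 0.787 | 0.47 | 1.08 |
| 1.5, then 0.4 | 0.783 | 0.781 | 1.57 | 0.36 |

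- The largest single-trial gap between the two PH fits was 1.4% in HR, or 0.08 of a standard error.
- Using 1, 3 or 5 df for the baseline moved the median HR by at most 0.007.
- In one trial of 20,000 patients per non-constant scenario, the gap was 0.1% or less.
- An odds-scale Royston-Parmar model gave a different measure: odds ratios of 0.574, 0.654 and 0.885 for the three non-constant rows.

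In the first two rows the single HR is nearly the same (0.615 and 0.606) although the effects are very different. The baseline-only fallback does not separate them; the treatment-by-time term does.

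**The case against.** A reader might infer that the fallback is bound to return the Cox hazard ratio. The documents do not support that. The SAP names a class of models, not a fitted specification. Royston-Parmar models can carry a time-dependent treatment effect or use an odds scale, and other parametric survival models include non-PH forms such as the log-logistic. None of these is excluded, and the declared purpose is to capture non-proportionality. This stands, and it limits the point to the stated rationale and what is left unspecified.

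A reader might also infer that nothing free of PH is planned. The per-arm Kaplan-Meier medians and 48-week estimates do not need PH. Only a between-arm contrast with a confidence interval is missing.

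Nor do the documents support saying that the primary test hangs on a diagnostic. Cox is the primary model, its treatment term gives the only test statistic, and the fallback is merely to be considered. The SAP implies this rule but does not state it for the case where the check fails.

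Finally, it is tempting to argue that events come so early that a failed check is likely. SAP 2.2.3 says that "46.1% of patients were readmitted within 3 months of initial hospitalisation", but this is national audit data in patients with raised eosinophils. The 51%, 59% and 64% at 6, 9 and 12 months are Leicestershire figures for all COPD admissions, so they do not form one curve. A falling event rate is in any case compatible with PH. A delayed onset of effect is an assumption that neither document makes.

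It is also fair to say that this is a conditional provision, and that the primary model, its test and the sample size stand as they are.

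**Conclusion.** The point holds in a limited form. The reason SAP 6.4.1 gives for its fallback is technically wrong. A hazard-scale Royston-Parmar model fitted for that reason reproduces the Cox hazard ratio to within about 1.4% in single trials of 238, even when the true effect is delayed, early or crossing. Unless a time-varying treatment effect or a non-PH scale is specified, the fallback does not do what it is there for, and the plan has no between-arm contrast with a confidence interval to use instead.

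That a baseline-only model on the hazard scale is still PH follows from the algebra and needs no assumption. The simulated figures rest on the assumed change at week 12, the assumed effect sizes, a constant control hazard and the assumed truncation. They illustrate the size of the problem and do not predict this trial. How likely the PH check is to fail cannot be judged from the documents.

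**What to change.** Replace the fallback paragraph in SAP 6.4.1 with one that does the following:

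- Corrects the rationale: the baseline is already free in Cox, and non-proportionality is handled by letting the treatment effect vary with time.
- States outright that the Cox treatment test remains the single primary test whatever the PH check shows.
- Specifies that, if PH is in doubt, a Royston-Parmar model with an explicit treatment-by-time term will be fitted, with scale, degrees of freedom and knots given, and hazard ratios reported at set times.
- Adds one between-arm summary that does not need PH, with a 95% CI: the difference in restricted mean event-free time to 48 weeks, or the Kaplan-Meier difference at 48 weeks. One is enough.

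The time-to-event secondary outcomes inherit the change through SAP 6.5.1.1. The cost is one SAP paragraph and a little more analysis with standard methods. Sample size, data collection and trial conduct do not change.
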